 - Dose Cohort 3: 1600 mg NOX66 (Days 1 to 14 [Cycle 1]) + EBRT (Days 2 to 11 of Cycle 1, depending on number of fractions to be administered). From Cycle 2 onwards, 1600 mg NOX66 will be administered on Days 1 to 7.
 - Dose Cohort 4: 2400 mg NOX66 (Days 1 to 14 [Cycle 1]) + EBRT (Days 2 to 11 of Cycle 1, depending on number of fractions to be administered). From Cycle 2 onwards, 2400 mg NOX66 will be administered on Days 1 to 7.
- Part 2: Eligible patients will be enrolled in 1 of 2 treatment arms:
 - Arm 1 patients with mCRPC: RP2D NOX66 (Days 1 to 14 [Cycle 1]) + EBRT (Days 2 to 11 of Cycle 1, depending on number of fractions to be administered). From Cycle 2 onwards, RP2D NOX66 will be administered on Days 1 to 7.
 - Arm 2 patients with BC and NSCLC: RP2D NOX66 (Days 1 to 14 [Cycle 1]) + EBRT (Days 2 to 11 of Cycle 1, depending on number of fractions to be administered). From Cycle 2 onwards, RP2D NOX66 will be administered on Days 1 to 7.

Patients will have a rest period (no NOX66 administration) on Days 15 to 21 of Cycle 1 and Days 8 to 14 of Cycle 2 onwards (Parts 1 and 2).

Study Assessments:

Efficacy will be assessed by evaluating the change from baseline PSA for patients with mCRPC. For all patients, DCR (as measured by complete response [CR], PR and SD) will also be evaluated based on change from baseline imaging using RECIST v1.1 criteria. Bone lesions will be evaluated using Prostate Cancer Working Group 3 (PCWG-3) criteria. Other assessments to be performed during this study are ECOG scores, pain severity, and Patient Reported Outcomes. Efficacy will also be evaluated by examining skeletal-related events (SREs), symptomatic skeletal events (SSEs), progression-free survival (PFS), overall survival (OS), and objective response rate.

Safety and tolerability of NOX66 and separately for both doses of EBRT (8 Gy or 20/25 Gy) will be determined by AEs, treatment-emergent adverse events (TEAEs), clinical laboratory evaluations, vital signs, 12-lead ECGs and physical examinations. The study will also evaluate DLTs during Cycle 1 of Part 1.

Plasma PK analysis for idronoxil and selected metabolites will be performed for Part 1 (all patients) and Part 2 (first 10 patients enrolled for each tumor type).

Changes from baseline in the lipidomic profile, plasma levels of cytokines and chemokines (all sites), and circulatory tumor deoxyribonucleic acid (ctDNA; all patients participating at pre-selected sites only) will be assessed (Parts 1 and 2).

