- * The procedures detailed at Cycle 5 Day 1 will be performed for all subsequent on-site visits (unless otherwise specified). Patients will continue NOX66 administration in each cycle from Day 1 until Day 7 followed by a 7-day rest period (Days 8 to 14).

It is important that PK sampling occurs as close as possible to the scheduled time. In order to achieve this, other assessments scheduled at the same time may be initiated prior to the timepoint. The order of assessments (as applicable to study visit) that should occur before dosing is: 1) PRO questionnaires, 2) vital signs, 3) ECG, 4) PK sampling, 5) dose administration. Blood sampling for safety laboratory assessments will be done prior to dosing. The order of assessments (as applicable to the study visit) that should occur after dosing is: 1) vital signs, 2) ECG, 3) PK sampling. All other procedures can be completed (as applicable to study visit) after the PK sample has been collected. It is critical that the patients record the time of dose in their Patient Study Drug Administration Diary for the PK assessment and the site record the time of blood sampling.

- ^{a.} End of Treatment Visit (EOT) occurs 7 to 10 days after the last dose of study drug. Assessments completed within 7 days prior to the last dose of study drug do not need to be repeated. If a patient discontinues from the study early (Early Discontinuation [ED]), they will have an ED Visit within 7 to 10 days after the last dose of study drug.
- ^{b.} For patients who permanently discontinue study drug for any reason other than confirmed disease progression, tumor imaging and disease response assessments will continue to be performed every 12 weeks (± 7 days) for up to 12 months after the last dose of the study drug until disease progression, withdrawal of consent, initiation of new anticancer therapy, the patient is lost to follow-up or death, whichever comes first.
 - If a patient meets disease progression during the follow-up period according to RECIST v1.1 criteria, a tumor imaging and disease response assessment is not required.
 - If a patient permanently meets clinical disease progression during the follow-up period, a tumor imaging and disease response assessment does not need to be repeated if completed ≤ 28 days after the date of clinical disease progression.
 - Patients who have met disease progression will be contacted every 3 months for survival follow-up.

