- ^{c.} An informed consent must be signed before any study procedures may be performed.
- ^d Patients will receive a Patient Study Drug Administration Diary for each cycle. Patients must record the date and time of each dose administration (Days 1 to 14 [Cycle 1] and Days 1 to 7 [Cycle 2 onwards]), as well as any missed doses.
- e. All patients will be contacted by phone 1 day prior to every on-site visit for assessing signs and symptoms of coronavirus disease 2019 (COVID-19) and if they had any contact with a person who has tested positive for severe acute respiratory syndrome coronavirus 2 (SARS-CoV-2). Patients will receive a follow-up phone call 30 days after last dose to follow-up on any ongoing AEs/SAEs.
- ^{f.} Medical history includes collection of data from any available historical genetic assays conducted to identify genetic variations. For mCRPC patients only: Gleason score assessment will also be collected as part of the medical history of the patient.
- ^g A complete physical examination, including weight, will be performed during the Screening Visit. A symptom-directed physical examination will be performed prior to the first dose of study drug in Cycles 1 to 3, and every second cycle thereafter (i.e., Cycles 5, 7, 9, 11 etc.; or within 3 days before Day 1 of the cycle) and at the EOT/ED Visit. Abbreviated physical examinations may be conducted as needed and will focus on new symptoms and will include examination of relevant systems as identified by the Investigator. Height will only be measured at Screening only. Weight will be measured at Screening,

Cycles 2, 5 and every second cycle thereafter (i.e., Cycles 7, 9, 11 etc.). Physical examinations need to include the assessment of the perineal and anal region.

- ^h Vital signs (oral or tympanic [both are accepted] temperature, pulse, respiratory rate and blood pressure) will be measured at Screening and during Cycle 1 at the following timepoints: predose and at 1 and 4 hours postdose on Days 1, 6 and 14. Vital signs will be measured predose on Day 1 of Cycles 1 to 3, every second cycle thereafter (i.e., Cycles 5, 7, 9, 11 etc.) and at the EOT/ED Visit.

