1.3.1 Electrocardiogram Schedule

Table 1-2	Electrocardiogram Schedule: Part 1 (All Patients) and Part 2 (Only
	for First 10 Patients in Each Tumor Type)

Sampling Time Point	Cycle 1 Day 1	Cycle 1 Day 2	Cycle 1 Day 6	Cycle 1 Day 14	Cycle 2 Day 1	Cycle 3 Day 1
Predose	\mathbf{X}^{\dagger}	Х	X^\dagger	X^\dagger	X^\dagger	\mathbf{X}^{\dagger}
1 hour (+ 15 minutes)	Х		Х	Х	Х	Х
2 hours (+ 15 minutes)	Х		Х	Х		
3 hours (+ 15 minutes)	Х		Х	Х		
4 hours (+ 15 minutes)	Х		Х	Х		
6 hours (+ 15 minutes)	Х		Х	Х		
8 hours (+ 15 minutes)	X ^a					
12 hours (+ 15 minutes)	X ^a					

† Within 30 minutes prior to dosing to allow for sitting blood pressure if needed.

^a Only for Part 1.

NOTE: For patients who will not undergo PK sampling in Part 2 of the study, a single ECG will be collected predose on Day 1 of each cycle up to Cycle 3.

After Cycle 3 Day 1, ECGs will be taken predose (within 30 minutes prior to dosing to allow for sitting blood pressure if needed) for all patients in both study parts, on Day 1 of every second cycle thereafter (i.e., Cycles 5, 7, 9, 11 etc.) and at the EOT/ED Visit.

1.3.2 Pharmacokinetic and Pharmacodynamic Sampling Schedule for Part 1 and Part 2

Table 1-3Pharmacokinetic Sampling Schedule Following Morning Dose –
Part 1 (All Patients) and Part 2 (Only for First 10 Patients in Each
Tumor Type)

Sampling Time Point	Blood Volume (mL)		Cycle 1 Day 2*	-	-	Cycle 1 Day 15**	•	Cycle 2 Day 8***	Cycl e 3 Day 1 ^b	Cycle 3 Day 8 ^{b,} ***
Predose (within 15 minutes prior to dosing)	1 × 4	х	х	Х	Х	Х	X	Xc	X	Xc
0.5 hour (± 5 minutes)	1×4	Х		Х	Х					
1 hour (± 5 minutes)	1×4	Х		Х	Х					
2 hours (± 5 minutes)	1×4	Х		Х	Х		Х		Х	
3 hours (± 5 minutes)	1×4	X		Х	Х					
4 hours (± 5 minutes)	1×4	Х		Х	Х					
6 hours (± 10 minutes)	1×4	Х		Х	Х					
8 hours (± 15 minutes) ^a	1 × 4	Х								
12 hours (\pm 30 minutes; Prior to evening dose) ^a	1×4	Х								

^{a.} Only for Part 1.

^{b.} Cycle 3 Days 1 and 8 samples only for patients in Part 2.

^{c.} Can be collected at home.

* Sample to be collected approximately 12 hours post Day 1 evening dose.

** Sample to be collected approximately 12 hours post Day 14 evening dose.

*** Sample to be collected approximately 12 hours post Day 7 evening dose.

Table 1-4	Pharmacodynamic Sampling Schedule – Part 1 and Part 2 (All
	Patients)

Assay	Blood Volume (mL)	Screening/Cycle 1 Day 1 Predose ^c			End of Treatment/Early Discontinuation
Chemokines, cytokines and lipids ^a	1 × 4	Х	Х	Х	Х

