2.3.3 Overall Benefit: Risk Conclusion

Considering the measures taken to minimize risk to patients participating in this study, the potential risks identified in association with NOX66 are justified by the anticipated benefits that may be afforded to patients with mCRPC and other solid tumors.

3 Objectives and Endpoints

Objectives	Endpoints				
Primary Objectives and Endpoints					
Part 1 (Dose Escalation):	The primary objective for Part 1 will be determined based on the count of DLTs.				
To determine the MTD and RP2D of NOX66 in combination with low-dose EBRT in patients with any	• MTD is defined as the dose level at which no more than 1 patient out of 6 experiences a DLT at the end of Cycle 1.				
solid tumor	• RP2D is the highest dose administered at which no more than 1 patient out of 6 experiences a DLT at the end of Cycle 1 and the dosage form, including the dosing frequency, is acceptable to patients.				

Table 3-1Objectives and Endpoints

Objectives	Endpoints
 Part 2 (Dose Expansion): Arm 1: To evaluate the effect of NOX66 on PSA response in patients with mCRPC. Arm 2: To evaluate the effect of NOX66 on DCR in patients with BC and NSCLC. 	 PSA response is defined as the proportion of patients with a reduction in PSA in plasma (ng/mL) of ≥ 30% from baseline at the end of Cycles 3 and 6. DCR is measured by the percentage of patients with a best overall confirmed response of CR or PR and SD.
Secondary	V Objectives and Endpoints
Characterize the safety and tolerability of NOX66	Safety and tolerability of NOX66 as determined by AEs, TEAEs, clinical laboratory evaluations, vital signs, 12-lead ECG and physical examinations.
Evaluate the safety and tolerability of both doses of EBRT	Safety and tolerability of both doses of EBRT as determined by AEs, TEAEs, clinical laboratory evaluations, vital signs, 12-lead ECG and physical examinations.
Evaluate the exposure of idronoxil	Concentration of idronoxil and selected metabolites in plasma and derived PK parameters, including but not limited to: C _{max} , T _{max} , AUC _(0-t) , AUC ₍₀₋₆₎ , AUC ₍₀₋₁₂₎ , AUC _(0-inf) , C _{min} and t ₂ , as data permit.

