 - Arm 1 patients with mCRPC: RP2D NOX66 (Days 1 to 14 [Cycle 1]) + EBRT (Days 2 to 11 of Cycle 1, depending on number of fractions to be administered). From Cycle 2 onwards, RP2D NOX66 will be administered on Days 1 to 7.
 - Arm 2 patients with BC and NSCLC: RP2D NOX66 (Days 1 to 14 [Cycle 1]) + EBRT (Days 2 to 11 of Cycle 1, depending on number of fractions to be administered). From Cycle 2 onwards, RP2D NOX66 will be administered on Days 1 to 7.

Patients will have a rest period (no NOX66 administration) on Days 15 to 21 of Cycle 1 and Days 8 to 14 of Cycle 2 onwards (Parts 1 and 2).

The study schemes are provided in Figure 1–1 (Part 1) and Figure 1–2 (Part 2), and the Schedule of Activities (SoA) is provided in Table 1-1 (Parts 1 and 2).

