8.2.6 Electrocardiograms

Triplicate 12-lead ECGs will be obtained in Parts 1 and 2 as outlined in the SoA (Table 1-1 [Parts 1 and 2]) using an ECG machine that automatically calculates the heart rate and measures PR, QRS, QT and QTc intervals.

For all patients in Part 1 and the first 10 patients in each tumor type for Part 2 who will undergo PK sampling, a series of ECGs (in triplicate, within 1 to 2 minutes apart) will be collected at Screening, and at the following timepoints (Table 1-2):

- Cycle 1:
 - Days 1, 6 and 14: predose (within 30 minutes prior to dosing to allow for sitting BP if needed) and at 1, 2, 3, 4 and 6 hours postdose (+ 15 minutes). Additionally, for Part 1 only, ECGs will also be taken on Day 1 at 8 and 12 hours postdose (+ 15 minutes).
 - Day 2: predose.

- Cycle 2 Day 1: Predose (within 30 minutes prior to dosing to allow for sitting BP if needed) and at 1 hour postdose (+ 15 minutes).
- Cycle 3 Day 1: Predose (within 30 minutes prior to dosing to allow for sitting BP if needed) and at 1 hour postdose (+ 15 minutes).

For patients in Part 2 who will not undergo PK sampling, a series of ECGs (in triplicate, within 1 to 2 minutes apart) will be collected at Screening, and a single ECG predose (within 30 minutes prior to dosing to allow for sitting BP if needed) will be collected on Day 1 of Cycles 1 to 3.

Electrocardiograms will be taken predose (within 30 minutes prior to dosing to allow for sitting blood pressure if needed) for all patients in both study parts on Day 1 of every second cycle thereafter (i.e., Cycles 5, 7, 9, 11 etc.) and at the EOT/ED Visit. Electrocardiograms will be obtained after 5 minutes of rest in the supine position.

Twelve-lead ECGs will be obtained after the patient has been resting supine for at least 5 minutes prior to the times indicated in the SoA. All ECGs should be recorded with the patient in the same physical position.

At each time point at which triplicate ECG recordings are required, three individual ECG tracings should be obtained as closely as possible in succession, within 1 to 2 minutes apart. The full set of triplicates should be completed in less than 4 minutes.

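### Part 2 patients outside the PK subset (34 to 40 of 64 to 70) have no scheduled ECG during a NOX66 dosing period; one existing ECG could be moved to Cycle 1 Day 14 post-dose

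*Combined protocol and SAP*

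**What the plan says.** Twelve-lead ECG is part of a secondary safety endpoint. Section 3, Table 3-1 lists "Safety and tolerability of NOX66 as determined by AEs, TEAEs, clinical laboratory evaluations, vital signs, 12-lead ECG and physical examinations".

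The ECG schedule has two tiers.

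- **All Part 1 patients and the first 10 Part 2 patients of each tumor type** (those with PK sampling) have triplicate ECGs at the times in Table 1-2. These include several post-dose times on Cycle 1 Days 1, 6 and 14, and 1 hour post-dose on Day 1 of Cycles 2 and 3.
- **The remaining Part 2 patients** have a triplicate at Screening. After that, the Table 1-2 NOTE says "a single ECG will be collected predose on Day 1 of each cycle up to Cycle 3". Section 8.2.6 agrees: the single pre-dose ECG "will be collected on Day 1 of Cycles 1 to 3".

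After Cycle 3, everyone has pre-dose ECGs "on Day 1 of every second cycle thereafter (i.e., Cycles 5, 7, 9, 11 etc.) and at the EOT/ED Visit". On the final visit, Table 1-1 footnote a says "End of Treatment Visit (EOT) occurs 7 to 10 days after the last dose of study drug".

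The dosing calendar in the Synopsis and Section 4.1 includes a "rest period (no NOX66 administration) on Days 15 to 21 of Cycle 1 and Days 8 to 14 of Cycle 2 onwards".

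Vital signs are planned differently. Table 1-1 footnote h and Section 8.2.5 require them "predose and at 1 and 4 hours postdose on Days 1, 6 and 14" of Cycle 1, with no restriction to PK patients.

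**The concern.** Put together, the ECG schedule and the dosing calendar place every ECG of a non-PK Part 2 patient before the first dose or about a week after the most recent one. An effect that follows exposure and fades in the rest week would be missed in that patient, however many cycles are given.

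The protocol treats QTc as relevant: Section 5.2 excludes patients with a screening QTcF above 470 msec. Section 2.3.1 reports no cardiac risk from initial clinical use. However, in the earlier EBRT study the highest dose was 1200 mg and treatment lasted up to 16 days (Section 4.2). The dose taken into Part 2 may be as high as 2400 mg and is given in repeated cycles until progression.

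What is at stake is detection in the individual patient. The group-level description of ECG effects has other sources.

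**Working it through.** No sample-size formula applies, because Section 9.1 says that no hypotheses are tested. The check is a calendar and a count.

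**1. The plan's own Arm 2 figure.** Section 9.2 gives 12 to 15 patients per tumor type in two tumor types: 2 × 12 = 24 and 2 × 15 = 30. This reproduces the stated 24 to 30.

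**2. Patients without PK sampling.**
- Part 2 total: 40 + 24 = 64, up to 40 + 30 = 70.
- PK subset (Section 8.5): 3 tumor groups × 10 = 30.
- Remainder: 64 − 30 = 34 (34/64 = 53.1%), up to 70 − 30 = 40 (40/70 = 57.1%).
- By tumor type: mCRPC 30/40 (75%); BC and NSCLC each from 2/12 (17%) to 5/15 (33%).

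**3. Time since the last dose at each scheduled ECG.** Cycle 1 has 14 days on and 7 off. Later cycles have 7 on and 7 off. Full drug-free days = ECG day − last dosing day − 1. Elapsed hours, from an evening dose to a morning visit, = 24 × (ECG day − last dosing day) − 12.

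| ECG | Study day | Last dosing day | Full drug-free days | Hours, about |
|---|---|---|---|---|
| Screening; Cycle 1 Day 1 pre-dose | up to 1 | none yet | – | – |
| Cycle 2 Day 1 pre-dose | 22 | 14 | 7 | 180 |
| Cycle 3 Day 1 pre-dose | 36 | 28 | 7 | 180 |
| Cycle 5 Day 1 pre-dose | 64 | 56 | 7 | 180 |
| Cycles 7, 9, 11 and on | every 28 days | 8 days earlier | 7 | 180 |
| EOT/ED | last dose + 7 to 10 | – | 6 to 9 | 156 to 228 |

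None of these falls inside a dosing period. Table 1-1 does mark ECGs under Cycle 1 Days 2 to 7 and Day 14, but footnote i limits those to patients with PK sampling.

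**4. Exposure at those times.** The documents give no half-life for idronoxil. As an assumption only, the fraction left after 180 hours is 2^(−180/half-life): 0.003% at 12 hours, 0.55% at 24 hours and 7.4% at 48 hours. Off drug is therefore exact for dosing and approximate for plasma exposure.

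**5. Are these patients on site on Cycle 1 Day 14?** Sections 1.1 and 4.1 have each patient attend on that day, with the morning dose given at the center. Vital signs at 1 and 4 hours post-dose and the Day 14 laboratory tests (Section 8.2.7) carry no PK restriction. A post-dose ECG there needs no new visit.

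**The case against.** The strongest reply is that the two tiers are a deliberate and adequate choice. Each Part 2 PK patient has 5 post-dose triplicates on each of three Cycle 1 days plus one in each of Cycles 2 and 3: 5 × 3 + 2 = 17. With 30 such patients and all of Part 1 (up to 30), the group-level question is covered in a descriptive study. Section 2.3.1 reports no increase in cardiac AEs so far and describes ECG analysis before and after the dosing period. That stands, and it limits the point to individual detection.

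A reader might infer that the by-arm summary mixes drug-free with on-drug tracings and so dilutes any effect. The documents do not support this. Section 9.4.7.1 summarizes ECG changes over time. Every time point shared by PK and non-PK patients (Screening, Day 1 pre-dose, EOT/ED) is off dosing for both, and every on-drug time point holds PK patients only. A table by time point mixes nothing. Dilution would need a summary such as worst post-baseline value, which the plan does not specify.

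A reader might also want the Cycle 3 and later Day 1 ECGs moved to after the dose. That goes too far. Section 6.4 places supervised dosing only on Cycle 1 Days 1, 2, 6 and 14 and Day 1 of Cycles 2 and 3, so from Cycle 5 on the change would need on-site dosing that the plan does not provide. At any cycle it would also remove the tracing taken before drug restarts. No time of peak concentration is given, and the product is described as slow and sustained release, so 1 hour after the first dose following a rest week might miss the relevant exposure.

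**Conclusion.** The point holds as a gap in scheduled coverage. Between 34 and 40 of 64 to 70 Part 2 patients (53% to 57%), including 30 of 40 with mCRPC, have no scheduled ECG in a NOX66 dosing period. The count assumes that enrollment reaches the planned sizes and that all 30 PK places are filled.

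Three stronger statements should not be read into it. The plan does not say that these patients never have an ECG on NOX66, because clinically prompted ECGs are not ruled out. It does not follow that their ECGs can show no drug effect, because a persistent or cumulative effect could appear off dosing. The gap is not always at least 7 full drug-free days, because the earliest EOT/ED visit leaves 6, or about 156 hours after an evening dose.

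What remains is that no scheduled tracing would find an acute on-treatment QTc, heart-rate or conduction effect in one of these patients. It is a modest weakness that can be remedied cheaply.

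**What to change.** In Table 1-1 footnote i, the Table 1-2 NOTE and Section 8.2.6, for Part 2 patients without PK sampling, move the single Cycle 2 Day 1 pre-dose ECG to Cycle 1 Day 14 post-dose, with the vital signs already due at 1 or 4 hours. Name one of the two times. Table 1-2 has an ECG slot at both on that day, so the result can be set beside that of the PK patients, although theirs is a triplicate. Keep the pre-dose ECGs at Cycle 1 Day 1 (baseline), Cycle 3 Day 1 and later visits as they are. State in Section 9.4.7.1 that ECG results are reported by time point.

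**Cost.** Wording in three places and one sentence in the analysis section. The number of ECGs and visits does not change. The off-dosing tracing at Cycle 2 Day 1 is lost for these patients. Because the documents give no time of peak concentration, one tracing at 1 or 4 hours is a check on treatment, not necessarily at peak exposure.

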2.1 Study Rationale

Idronoxil, which is the active ingredient of the NOX66 formulation, is a synthetic flavonoid derivative of genistein that inhibits external Ecto-NOX disulfide-thiol exchanger (ENOX) 2 to induce apoptosis². ENOX2 inhibition activates the sphingomyelinase pathway and deactivates the antiapoptotic protein kinase B (Akt) pathway, a key driver of radiotherapy resistance. The targeted effect on ENOX2 has the potential to limit toxicity to non-cancer cells, which preferentially express ENOX1. Previous studies have demonstrated improved radiation sensitivity in prostate cancer with flavonoid derivatives. Early studies of intravenous and oral formulations of idronoxil were hampered by limited bioavailability.¹ The Sponsor has sought to address the problem of extensive drug metabolism through the development of a rectal suppository dosage form. With blood draining from the distal part of the rectum directly into the inferior vena cava, first pass liver metabolism can be avoided. In the case of a diphenolic drug such as idronoxil, the bioavailability is augmented by the rectal mucosa being known to be devoid of transferase activity and therefore the phase II metabolism is significantly reduced. These two aspects combined are the basis for the rationale that idronoxil delivered via the rectum is subjected to less phase I and phase II metabolism than that observed for orally administered idronoxil. NOX66 is a suppository dosage form of idronoxil in a proprietary fatty base containing a surfactant. This formulation is novel in that a lipophilic active ingredient is dispersed in a lipophilic suppository base - compared with traditional suppository formulations whereby a hydrophilic base would normally be utilized. Moreover, this suppository dosage form provides a slow and sustained release of idronoxil comparable to an intravenous infusion.²

The first clinical study with NOX66 (NOX66-001A) was a Phase 1a/1b study in which NOX66 was evaluated both as a monotherapy and in combination with carboplatin, in patients with refractory solid tumors. Two breast cancer (BC) patients and one ovarian cancer patient enrolled in this study had reductions in target lesions size with one BC patient showing target lesion disappearance (as per Response Evaluation Criteria in Solid Tumors [RECIST] v1.1.) at the end of the study.

